Official Title of the Study:

A Prospective Randomized Clinical Trial to Evaluate the Impact of Intraoperative Ventilation with High Oxygen Content on the Extent of Postoperative Pneumocephalus in Patients Undergoing Craniotomies

NCT number: NCT02722928

Last approved continuing review on: 08MAR2018

IRB protocol number: 2015H0032

- Initial submission approved on: 27JAN2015
- IRB confirmed closure date: 26DEC2018

Objectives*Primary Objective*

We compared the rate of occurrence and volume of postoperative pneumocephalus in patients undergoing craniotomies (hemispheric or posterior cranial fossa tumors and microvascular decompression) and receiving intraoperative ventilation with pure oxygen versus a conventional air/oxygen 1:1 mixture during the last stage of surgery (hemostasis and wound closure)

Secondary Objectives

We compared the incidence and volume of postoperative pneumocephalus in patients undergoing surgery in sitting and supine positions. Furthermore, we compared postoperative neurological outcomes and intensive care unit length of stay among neurosurgical patients (posterior cranial fossa tumors, supratentorial tumors, and transsphenoidal /endoscopic procedures)

Study Design

We conducted a prospective randomized single-blinded study at The Ohio State University Wexner Medical Center enrolling patients (≥ 18 years) with an American Society of Anesthesiologists (ASA) physical status of II–IV undergoing neurosurgeries (supra- and infratentorial tumors such as astrocytomas and glioblastoma multiforme, and microvascular decompression) in sitting, prone, lateral, park bench, and other positions.

Sample Size and Statistical Analysis

We estimated that a sample size of 80 patients per group would confer a greater than 80% power to detect a 20% decrease in volume in the intervention group with an alpha of 0.05 considering a mean pneumocephalus volume of 87 ml in the control group (standard deviation of 40). The sample size was estimated based on published data. Our proposed intervention is considered harmless, being applied routinely in perioperative settings. No intervention-related adverse events were expected during the study.

Categorical variables were reported as frequencies and percentages and compared between randomization groups using Chi-square tests or Fisher's exact tests where relevant. Continuous variables were reported as means and standard deviations or medians and interquartile ranges and compared between randomization groups using Student's t-tests or Wilcoxon rank sum tests where relevant. Hypothesis testing was conducted at a 5% type 1 error rate ($\alpha=0.05$). All statistical analyses were performed using SAS version 9.4 (SAS Institute, Cary, NC).

Randomization

The study was planned and conducted according to all the required institutional and state regulations related to clinical research. Patients were randomly distributed (random table) into two groups:

- Control Group (A): received controlled ventilation throughout the surgery with a conventional air/oxygen 1:1 gas mixture (FiO_2 60%)
- Interventional Group (B): received controlled ventilation with a conventional air/oxygen 1:1 gas mixture from the beginning of the surgery and during the tumor removal phase. However, patients in group B were switched to controlled ventilation with

100% O₂ once the tumor resection was completed and hemostasis started until extubation

Study Procedures

Both groups received supplemental oxygen via nasal cannula as a standard of care during the early postoperative period. A standard CT scan was performed within 6 hours post-surgery for both groups. CT scans were assessed and interpreted by a blinded radiologist in order to diagnose the frequency and the extent of postoperative pneumocephalus (quantification). TeraRecon Intuition software version 4.4.11.265.8092 was used, retrieving the CT scan data from the system and loading it into the software program. All CT data maintained a 1 mm slice increment. The air in the skull was identified and circled using a region of interest (ROI) tool. The area defined for measurements applied in this study was within the skull in any space occupied by brain. This excluded any air trapped between the bone from graft placement or between the skin and the skull. Once all the visually identified areas of “air” were circled and then selected within the skull, a Hounsfield unit (HU) threshold tool was used to remove any excluded tissue. The setting of -150 HU or less was applied, and the selected areas were presented in 2D and 3D. Only the areas identified within the ROI accounted for the 3D image. The volume was calculated in cm³ using the software presented by clicking the “volume” measurement tool. Considering similarity of the groups and randomization, it was expected that the duration of the last part of surgery and the lapsing time from the end of surgery to postoperative CT acquisition to be the same for the control and treatment groups. The following data was considered for intergroup analysis and selection bias exclusion: demographics (age, gender, weight, and body mass index), oxygen inhalation time, the period of time elapsed from the end of surgery to CT scan completion. The occurrence of adverse events and neurological status were assessed before the CT scan and compared with the baseline evaluation. Stage 1 was defined as the interval of time (minutes) measured from skin incision to the onset of hemostasis (i.e. after tumor removal). Stage 2 was defined as the interval of time (minutes) measured from the onset of hemostasis to incision closure. We conducted study intervention (for group B) during stage 2.

DISCUSSION

Our prospective randomized study is the first to examine the prophylactic effect of normobaric hyperoxygenation on limiting the extension of postoperative pneumocephalus volume in patients undergoing elective neurosurgery. A total of 70 patients were included into our final analysis. The study showed no pneumocephalus volume reduction when higher oxygen concentration (FiO₂ 100% vs 60%) was used prophylactically during the last stage of surgery in patients undergoing craniotomy (p= 0.47). We estimated that our intervention would produce a 20% decrease in pneumocephalus volume for the interventional group. However, after enrolling 105 (N=105) patients, an unanticipated blinded analysis showed that the variability relative to the pneumocephalus volume mean was much higher than initially assumed based on published data. Therefore, we determined that our study was underpowered and an unfeasible number of patients would have been required (N>400 patients/group) to be enrolled in order to detect the expected difference between groups.

Figure 1. CONSORT Flow Diagram

[figure not shown]

Table 1. Demographic and Clinical Variables

| Variable | Control n= 39 | Intervention n= 31 | p value |
|-------------------------------------|--------------------------|-------------------------------|----------------|
| Age (mean ± SD) | 46.69 (14.21) | 50.81 (13.28) | 0.2198 |
| Gender n (%) | | | |
| • Female | 23 (58.97) | 14 (45.16) | 0.2501 |
| • Male | 16 (41.03) | 17 (54.84) | |
| Race n (%) | | | |
| • White | 36 (92.31) | 27 (87.10) | 0.6916 |
| • African-American | 3 (7.69) | 4 (12.90) | |
| Biometrics mean ± SD | | | |
| • Weight (Kg ± SD) | 89.00 (21.69) | 94.00 (17.67) | 0.3034 |
| • Height (cm ± SD) | 168.31 (10.29) | 172.30 (10.90) | 0.1208 |
| • BMI (Kg/m ² ± SD) | 31.35 (7.42) | 31.94 (6.64) | 0.7301 |
| ASA n (%) | | | |
| • I | 0 (0.00) | 1 (3.23) | 0.8874 |
| • II | 12 (30.77) | 9 (29.03) | |
| • III | 26 (66.67) | 20 (64.52) | |
| • IV | 1 (2.56) | 1 (3.23) | |
| Preoperative Diagnosis n (%) | | | |
| • Supratentorial lesion | 25 (64.10) | 21 (67.74) | 0.7500 |
| • Infratentorial lesion | 14 (35.90) | 10 (32.26) | |

n = number of patients; ASA = American Society of Anesthesiologists

Table 2. Perioperative Variables

| Variable | Control n= 39 | Intervention n= 31 | p value |
|---|-----------------------------|-------------------------------|--------------------|
| Surgical Positioning n (%) | | | |
| Sitting | 1 (2.56) | 0 (0.00) | 0.1233 |
| Semi-sitting | 0 (0.00) | 0 (0.00) | |
| Prone | 10 (25.64) | 3 (9.68) | |
| Lateral | 7 (17.95) | 11 (35.48) | |
| Park bench | 0 (0.00) | 0 (0.00) | |
| Supine | 21 (53.85) | 17 (54.84) | |
| Procedure Performed n (%) | | | |
| Conventional Anterior Fossa | 23 (58.97) | 16 (51.61) | 0.1535 |
| Conventional Posterior Fossa | 15 (38.46) | 11 (35.48) | |
| Conventional Middle Fossa | 0 (0.00) | 3 (9.68) | |
| Minimally Invasive Anterior Fossa | 0 (0.00) | 1 (3.23) | |
| Minimally Invasive Middle | 1 (2.56) | 0 (0.00) | |
| Ventilatory parameters | | | |
| beginning of stage 2 [median and IQR] | | | |
| Ppeak (cm H ₂ O) | 21.0 [19.0 – 25.0] | 22.0 [20.0 – 25.0] | 0.3734 |
| PEEP (cm H ₂ O) | 4.9 [4.0 – 5.0] | 5.1 [4.4 – 7.0] | 0.0215 |
| EtCO ₂ (mm Hg) | 29.0 [28.0 – 32.0] | 30.00 [28.0 – 32.0] | 0.8726 |
| Length of stage 1 [median and IQR] | 177.0 [140.0 – 223.0] | 256.0 [145.0 – 344.0] | 0.0596 |
| Length of stage 2 [median and IQR] | 49.0 [34.00 – 63.0] | 55.0 [39.0 – 68.0] | 0.3688 |
| Postoperative Recovery Location | | | |
| PACU | 6 (15.38) | 3 (9.68) | 0.7214 |
| SICU | 33 (84.62) | 28 (90.32) | |
| Length of PACU stay (min ± SD) | 344.67 (455.51) | 178.33 (147.60) | 0.5683 |
| Length of SICU stay (min ± SD) | 1,380.0 [1,112.0 – 2,096.0] | 1,524.5 [1,312.0 – 2,814.5] | 0.1880 |
| End of Surgery - CT scan interval time in minutes [median and IQR] | 89.0 [61.0 – 125.0] | 80.0 [62.0 – 127.0] | 0.8229 |
| Postoperative pneumocephalus in cm³ [median and IQR] | 9.65 [3.61 – 23.20] | 7.06 [2.70 – 20.1] | 0.4768 |

n= number of patients; *Ppeak*= peak inspiratory pressure; *PEEP*= positive end-expiratory pressure; *EtCO₂*= end-tidal CO₂; *PACU*= post-anesthesia care unit; *SICU*= surgical intensive care unit; *CT*= computed tomography

Table 3. *Postoperative Pneumocephalus Volume in cm³ [median and IQR] according to Procedure Performed*

| Conventional Anterior Fossa | Control n= 23 | Intervention n= 16 | p value |
|-------------------------------------|-------------------------|------------------------------|----------------|
| | 17.40 [6.89 – 24.40] | 13.95 [4.82 – 22.15] | 0.4797 |
| Conventional Posterior Fossa | Control n= 15 | Intervention n= 11 | p value |
| | 4.38 [0.81 – 10.50] | 4.00 [0.60 – 13.00] | 0.8775 |

Table 4. *SICU LOS according to Procedure Performed (median min [IQR]).*

| Conventional Anterior Fossa | Control n= 23 | Intervention n= 16 | p value |
|-------------------------------------|--------------------------|------------------------------|----------------|
| | 1380 [1112.0 – 1665.0] | 1489.0 [1337.0 – 2814.5] | 0.2017 |
| Conventional Posterior Fossa | Control n= 9 | Intervention n= 9 | p value |
| | 2059.0 [1102.0 – 3049.0] | 1342.0 [1203.0 – 1665] | 0.7943 |

SICU= surgical intensive care unit; LOS= length of stay

Table 5. Changes in Neurological Outcomes at POD 3 Compared to Preoperative Evaluation

| Neurological Outcome Variation n (%) | Control n= 39 | Intervention n= 31 | p value |
|---|-------------------------|------------------------------|-----------------------|
| Improvement | 8 (20.5) | 6 (19.3) | 0.23 |
| No changes | 25 (64.1) | 15 (48.4) | |
| Deterioration | 6 (15.4) | 10 (32.3) | |

POD= postoperative day; n= number of patients

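### The stated power of more than 80% at 80 per group is about 78% on a two-sided test with common SD 40, and no loss allowance is stated; at the reported yield (70 of 105) it would be 60% to 72%

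*Combined protocol and SAP*

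**What the plan says.** The section Sample Size and Statistical Analysis of the combined protocol and SAP states: "We estimated that a sample size of 80 patients per group would confer a greater than 80% power to detect a 20% decrease in volume". The inputs are alpha 0.05 and the control-group values: "considering a mean pneumocephalus volume of 87 ml in the control group (standard deviation of 40". The analysis paragraph adds: "Hypothesis testing was conducted at a 5% type 1 error rate", and names Student's t-test or the Wilcoxon rank sum test for continuous variables. Nothing says whether the test is one- or two-sided, what SD was assumed in the intervention group, or how many patients were expected to lack an analysable volume.

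The Discussion reports that 105 patients had been enrolled when a blinded look was made, and: "A total of 70 patients were included into our final analysis". Tables 1 and 2 show these as 39 control and 31 intervention. The Discussion says that variability relative to the mean was much higher than planned, and concludes: "Therefore, we determined that our study was underpowered and an unfeasible number of patients would have been required (N>400 patients/group) to be enrolled". The readable text does not mention the 35 patients who were enrolled but not analysed. The CONSORT diagram may explain them, but it is not shown in the text available for this review.

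**The concern.** A power statement refers to patients who contribute an outcome. If 80 per group is read as the number to enrol, any loss lowers the power, and the plan states no allowance for loss. The margin is also thin or absent before any loss, depending on sidedness and SD, neither of which is stated.

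Two things are at stake. First, a reader takes more than 80% as a property of the design, although the usual reading of the stated inputs does not give it. Second, a team planning a successor trial from the Discussion would learn that the SD must be corrected, but not that one enrolled patient in three did not reach the analysis. If the figure of more than 400 per group counts patients analysed and is taken as an enrolment target, the new trial would again be too small.

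**Working it through.** **Inputs.** From Sample Size and Statistical Analysis: n = 80 per group, control mean 87 ml, SD 40, 20% decrease, alpha 0.05. From the Discussion: 105 enrolled, 70 analysed (39 and 31 in Tables 1 and 2), more than 400 per group needed. Assumed, because not stated: 1:1 allocation, and three readings of sidedness and SD.

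**Effect.** 0.20 × 87 = 17.4 ml. With SD 40 in both arms, d = 17.4/40 = 0.435. If the SD shrinks with the mean, the intervention SD is 0.8 × 40 = 32, the pooled SD is √((40² + 32²)/2) = 36.2, and d = 17.4/36.2 = 0.480.

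**The plan's own figure.** Normal approximation, two-sided, common SD:
- Power = Φ(d√(n/2) − 1.96) = Φ(0.435 × √40 − 1.96) = Φ(0.79) = 78.6%.
- n for 80% power = 2 × ((1.96 + 0.84)/0.435)², which rounds up to 83 per group.

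The noncentral t, which suits a t-test, gives 78.1% at 80 per group and needs 84 per group for 80%. So the figure is reproduced to within two points, but power is not above 80% on this reading.

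**Yield.** 70/105 = 66.7%, a loss of 33.3% (95% Wilson interval 25% to 43%). Applied to 2 × 80 = 160 enrolled: 160 × 0.667 ≈ 107 analysed, or about 53 per group.

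**Power on the planning inputs (noncentral t).**

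| Reading | 80 per group | 53 per group | Smallest n per group for 80% |
|---|---|---|---|
| Two-sided, SD 40 in both arms | 78% | 60% | 84 |
| Two-sided, SDs 40 and 32 | 86% | 69% | 69 |
| One-sided 5%, SD 40 in both arms | 86% | 72% | 67 |

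The projected loss costs 14 to 18 points. The second and third readings tolerate losses of about 14% (1 − 69/80) and 16% (1 − 67/80), but not one third. Over the Wilson interval for the loss (60 to 46 analysed per group), the first reading gives 66% to 54%.

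**Share due to variability.** Assume that 400 analysed per group gives 80% two-sided power for a 20% decrease. The coefficient of variation is then 0.20/((1.96 + 0.84) × √(2/400)) ≈ 1.01, against 40/87 = 0.46 in the plan. At 1.01:
- 80 per group: 24% power (78% at the planned variability)
- 53 per group: 17%
- 39 and 31, as analysed: 13%

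Variability takes away 54 points (78 to 24), and the projected loss a further 7 (24 to 17).

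**The figure of 400.** If it counts patients analysed, enrolment at this yield is 400/0.667 = 600 per group. If 400 were enrolled, 400 × 0.667 ≈ 267 would be analysed, and power at a coefficient of variation of 1.01 would be about 63%.

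**The case against.** The strongest case against the point has four parts.

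1. *The yield is a projection.* The text says that 105 were enrolled at the blinded look. It does not say that 105 were randomised or that this was the final count. Without the flow diagram, the 35 could have left before randomisation, in which case the randomised groups were not eroded. The Wilson interval does not cover this ambiguity. Nor is a planned enrolment of 160 stated: 80 per group appears only in the power statement and may mean patients analysed. All of this stands, so the figures at 53 per group must be conditional. It does not affect the 78%, which involves no loss.

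2. *A reader might infer that more than 80% holds exactly when all 80 per group are analysed.* The inputs do not support that on any of the three readings. Two-sided with common SD 40, the figure is missed with no loss at all; on the other two it survives a loss of about 14% to 16%. A reader might also take 60% as the answer, but it is the least favourable of the three readings, and the plan does not say which it used.

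3. *A reader might infer that the Discussion blames the wrong cause.* It does not. On its own figure of 400 per group, variability is by far the larger cause, and its conclusion of infeasibility is the same at 400 or 600. More than 400 is a lower bound, and the text does not say whether it already allows for loss. What stands against the Discussion is an omission only.

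4. *A planning estimate should not be overwritten with a yield seen at the end.* That is right, and the fix respects it. Table 2 also shows a control median of 9.65 cm³ against a planning mean of 87 ml, so power for a 17.4 ml fall describes the plan and not the population that was studied.

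**Conclusion.** The point holds in a limited form. On a two-sided t-test with SD 40 in both arms, the stated power is about 78% with every patient analysed, and 84 per group would be needed for 80%. That shortfall is small, and it depends on sidedness and SD assumptions that the plan does not give; one-sided, or with SDs 40 and 32, the claim is met at 80 per group.

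No allowance for patients not analysed is stated. If the yield of 70 in 105 applied to 160 enrolled, power on the planning inputs would be 60%, 69% or 72% by reading, below 80% on each. This rests on reading 80 per group as enrolled, and on the loss of 35 being of a kind that would recur.

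The documents do not support the view that loss, rather than variability, explains the low power. Loss is a second contributor that the readable text does not name.

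**What to change.** In Sample Size and Statistical Analysis, keep the planning statement as a record of how the trial was sized, and add the following:
- 80 per group means patients analysed.
- State the sidedness and the SD assumed in each arm.
- If the test was two-sided with common SD 40, correct the power to about 78%.
- Say that no loss allowance was made, if that is so, and give the power at the observed yield: about 53 analysed per group, 60% to 72% by reading.

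In the Discussion, keep higher variability as the dominant cause, and add that 35 of 105 enrolled patients were not analysed, with a pointer to the reasons in the flow diagram. Say whether the figure of more than 400 per group counts patients analysed or enrolled. If analysed, add that about 600 per group would have to be enrolled at this yield.

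The cost is a short recalculation and some wording. No extra patients and no change of conduct are asked for. The stated power becomes less favourable.

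### Does 80 patients per group really give more than 80% power, when the usual two-sided t-test with SD 40 in both arms gives about 78%?

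*Combined protocol and SAP*

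**What the plan says.** The section Sample Size and Statistical Analysis contains the only power statement for the planned design. For 80 patients in each arm it claims "greater than 80% power to detect a 20% decrease in volume in the intervention group with an alpha of 0.05". The inputs follow in the same sentence: "considering a mean pneumocephalus volume of 87 ml in the control group (standard deviation of 40", in ml. The section adds that the size was estimated from published data, which it does not identify.

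The analysis paragraph of the same section repeats the level ("Hypothesis testing was conducted at a 5% type 1 error rate") and says that continuous variables are "compared between randomization groups using Student's t-tests or Wilcoxon rank sum tests where relevant".

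Four things are not stated: whether the power calculation was one- or two-sided, which test it assumed, the SD in the intervention arm, and whether 80 counts enrolled or analysed patients.

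**The concern.** A reader checking a sample size for two means will usually assume a two-sided 5% t-test and one common SD. With the printed inputs that gives about 78%, not more than 80%. The plan states a lower bound rather than a rounded value, so 78% does not satisfy it, and no stated assumption closes the gap. If the default was in fact used, the trial's only power figure is slightly overstated and the target is 3 or 4 patients per group too small. If another assumption was used, a reader cannot tell which.

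**Working it through.** **Inputs from the plan.** Control mean 87 ml, decrease 20%, SD 40 (printed beside the control mean), 80 per group, alpha 0.05.

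**Inputs that have to be assumed.** Sidedness, test and intervention-arm SD.

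**Effect.** 0.20 × 87 = 17.4 ml. With a common SD of 40 the standardised difference is 17.4 / 40 = 0.435.

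**Default reading: two-sided, SD 40 in both arms.**
- Standard error = 40 × √(2/80) = 6.325.
- Normal approximation: 17.4 / 6.325 − 1.960 = 0.791, and Φ(0.791) = 0.786.
- Noncentral t with 158 degrees of freedom: 0.781.
- Patients per group for 80% power, normal: 2 × (1.960 + 0.842)² × 40² / 17.4² = 82.96, so 83. With the t distribution, 83 per group give 79.6% and 84 give 80.0%, so 84.
- Difference detectable with 80% power at 80 per group (t): 17.83 ml, which is 20.5% of 87.

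This reading does not reproduce the stated bound. It falls short by 80 − 78.1 = 1.9 percentage points.

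**Readings that do reproduce it.** Each changes one unstated assumption, except the last, which changes the scale as well as the SD. Powers are from the t distribution with 80 per group.

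| Assumption | Power |
|---|---|
| Two-sided, SD 40 / 40 (default) | 78.1% |
| Two-sided, SD 40 control, 38 intervention | 80.1% |
| Two-sided, SD 40 control, 32 intervention | 85.5% |
| One-sided 0.05, SD 40 / 40 | 86.3% |
| Two-sided on the log scale, coefficient of variation 40/87 = 0.46 in both arms (lognormal shape assumed) | 89.3% |

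For the third row, 32 is 0.80 × 40: the SD falls in proportion to the mean. The standard error is √((40² + 32²)/80) = 5.727, and the normal approximation is Φ(17.4 / 5.727 − 1.960) = Φ(1.078) = 0.860, close to the t value. With the control SD held at 40, the two-sided t-test reaches 80% once the intervention SD is about 38.1 or less.

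For the last row, the log SD is √ln(1 + 0.46²) = 0.438 (using the unrounded ratio) and the log difference is −ln 0.80 = 0.223.

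**Precision of the inputs.** The mean and SD are printed as whole numbers. Under the most favourable rounding (about 87.5 and 39.5, an assumption), the default reading gives 17.5 ml and 79.5% by the t distribution. Rounding removes most of the gap but, on that calculation, not all of it.

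**Is two-sided the right default?** Recomputing two-sided t-tests from the means and SDs in Table 1 (39 and 31 patients):

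| Variable | Recomputed p | Printed p |
|---|---|---|
| Age | 0.2192 | 0.2198 |
| Weight | 0.3029 | 0.3034 |
| Height | 0.1211 | 0.1208 |
| BMI | 0.7304 | 0.7301 |

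The reported baseline tests were two-sided. This makes the one-sided reading of the power calculation the least likely of the alternatives. It has no bearing on the unequal-SD or log-scale readings.

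**The case for a change.** The strongest case for asking for a change is that a lower bound was stated, the ordinary calculation misses it, and each assumption that rescues it has to be supplied by the reader. The Table 1 p-values support two-sided testing, and a common SD is the textbook convention. In addition, if 80 meant enrolled patients, any loss before analysis would take power below 78% on the default reading. The Discussion gives 105 enrolled and 70 analysed, so losses were not negligible. If the test were a Wilcoxon on normally distributed data, power would be about 76%.

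Much of this stands. The arithmetic is correct, and a fuller statement of assumptions would have been better practice. What does not stand is the step from a bound missed under one reading to a wrong figure. The plan itself places the SD "in the control group (standard deviation of 40" and frames the effect as a proportion. For a volume that cannot be negative, an SD that falls with the mean is an ordinary assumption, and a fall from 40 to 38 is enough. The source data are not identified, so the second SD or the analysis scale may have come from there. The question of enrolled or analysed patients is a separate omission and does not show that the power figure was miscalculated.

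**Conclusion.** The concern does not call for a change. The calculation is under-described: power lies between about 78% and 89% across the t-test readings above, and the stated bound holds in all of them except a common SD of 40 with a two-sided test. In that case the shortfall is 1.9 percentage points, or 3 to 4 patients per group. The documents do not say which reading was used, so they do not establish an error. A remedy would either write down a missing assumption or restate a figure that has not been shown to be wrong.

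Neither would alter a result. The Discussion reports that variability relative to the mean was much higher than assumed, that the study was underpowered, and that more than 400 patients per group would have been needed. Table 2 gives median volumes of 9.65 and 7.06 cm³, far from the planning mean of 87 ml even allowing for the difference between a median and a mean. Beside that, three or four patients per group are immaterial, and the study is closed.

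This conclusion rests on accepting an intervention-arm SD modestly below 40 as a plausible planning assumption. Evidence that a common SD of 40 and a two-sided t-test were used would make the accurate statement about 78%, with the same lack of consequence.

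### The secondary objectives compare patient groups, but the plan and Tables 1 to 5 test only control against intervention, so on that reading no analysis answers them

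*Combined protocol and SAP*

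**What the plan says.** The Secondary Objectives contain two statements. The first is about position: "We compared the incidence and volume of postoperative pneumocephalus in patients undergoing surgery in sitting and supine positions". The second says that "we compared postoperative neurological outcomes and intensive care unit length of stay among neurosurgical patients", with three groups in parentheses: "posterior cranial fossa tumors, supratentorial tumors, and transsphenoidal /endoscopic procedures".

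The Sample Size and Statistical Analysis section gives one rule for each type of variable. Categorical variables are "compared between randomization groups using Chi-square tests or Fisher's exact tests where relevant". Continuous variables are "compared between randomization groups using Student's t-tests or Wilcoxon rank sum tests where relevant". It describes no model, covariate adjustment, stratified analysis or interaction.

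The tables follow that rule. Table 3 (volume) and Table 4 ("SICU LOS according to Procedure Performed") repeat the arm comparison separately within conventional anterior fossa and conventional posterior fossa procedures. Table 5 compares neurological change by arm over all 70 patients.

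**The concern.** An objective that compares types of patient needs a contrast between those types. A test of control against intervention does not supply one, whether run overall or inside a single procedure. On the between-group reading, the plan followed to the letter leaves both secondary objectives unanswered, although the data for part of the second are in hand.

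The objectives can also be read as asking for the arms to be compared within each group. That reading is only partly served. Neurological outcome is never split by group, no transsphenoidal/endoscopic group appears, and the procedure split omits some categories.

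At stake are the secondary results. A reader who looks for the comparison the objectives announce finds p values that answer a different question.

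**Working it through.** **1. The plan's own figure.** The only design calculation is for volume between arms: 80 per group, SD 40 ml, difference 0.20 × 87 = 17.4 ml. The standard error is 40 × √(2/80) = 6.32 and 17.4/6.32 = 2.75. Power is Φ(2.75 − 1.96) = 78.6% two-sided, or Φ(2.75 − 1.645) = 86.6% one-sided, against a stated figure above 80%. That figure is not at issue here, and it does not cover any comparison between patient groups.

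**2. What the printed p values compare.** Recomputing from the printed counts confirms that the rows on site, position and neurological outcome are arm comparisons.
- Table 1, diagnosis (25/14 control, 21/10 intervention): chi-square 0.10 on 1 df, p = 0.750; printed 0.7500.
- Table 2, position (sitting, prone, lateral, supine: 1, 10, 7, 21 control; 0, 3, 11, 17 intervention): Fisher's exact p = 0.1233; printed 0.1233. This tests whether position is balanced between arms. It does not compare pneumocephalus between positions.
- Table 5 (8/25/6 control, 6/15/10 intervention): chi-square 2.91 on 2 df, p = 0.233; printed 0.23.

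Every other p value in Tables 1 to 5 stands against a control and an intervention column. Tests between positions, sites or procedures: 0. Interaction tests: 0.

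**3. Objectives against analyses.**

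| Objective | Groups in the data | Analysis reported |
|---|---|---|
| Incidence and volume by position | Sitting 1 + 0 = 1; supine 21 + 17 = 38 | None; no table gives incidence |
| Neurological outcome by group | Supratentorial 25 + 21 = 46; infratentorial 14 + 10 = 24 | Table 5, by arm, not split |
| Intensive care stay by group | As above | Tables 2 and 4, by arm; Table 4 within two procedures |
| Transsphenoidal/endoscopic | No such row | None |

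Table 2 has two minimally invasive patients (1 anterior, 1 middle). The documents do not say whether these were endoscopic.

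**4. Coverage of Tables 3 and 4.** Table 2 lists five procedure categories. Conventional anterior (23 + 16 = 39) and posterior (15 + 11 = 26) make 65 of 70 patients; the other three categories hold 5. Table 4 has 39 anterior but only 9 + 9 = 18 posterior patients, so 26 − 18 = 8 posterior patients are absent (6 control, 2 intervention). Table 2 sends 6 control and 3 intervention patients to PACU, which fits those 8 never entering the SICU. SICU stay is therefore observed in a subset related to site.

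**5. Sitting against supine.** With one sitting patient among 39, the extreme rank has probability 1/39. The smallest two-sided exact rank-sum p is 2/39 = 0.051, so the volume comparison cannot reach 0.05 whatever the data. The sitting patient is a control; within that arm the minimum is 2/22 = 0.091. Incidence in one patient can only be 0% or 100%.

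**6. What a site comparison can deliver.** Deterioration has 6 + 10 = 16 events in 70 (22.9%). Assuming a common rate and ignoring arm, the standard error of the 46 against 24 difference is √(0.229 × 0.771 × (1/46 + 1/24)) = 0.106. The 95% half-width is about 21 percentage points.

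**7. Whether the separate p values show differing effects.** In Table 4 the median differences are 1489 − 1380 = +109 min ("1489.0 [1337.0 – 2814.5] | 0.2017") and 1342 − 2059 = −717 min ("1342.0 [1203.0 – 1665] | 0.7943"). An interaction could be approximated from these using log medians, SD = ln(Q3/Q1)/1.349 and variance inflated by π/2. The same method can be checked against the printed arm p values:
- anterior: ln(1489/1380) = 0.076, SE 0.190, p = 0.69; printed 0.2017
- posterior: ln(1342/2059) = −0.428, SE 0.331, p = 0.20; printed 0.7943

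It misses in both rows, in opposite directions, so interaction figures built this way should not be relied on.

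**The case against.** The strongest reply is that the second objective lists types of patient only to describe the study population. On that reading, the overall arm comparisons of SICU stay (Table 2) and neurological change (Table 5) answer it. The wording permits this, and it is why the conclusion is tied to a reading. It does not rescue the position objective, which names two groups, nor account for a listed group that no table reports.

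A second reply is that more analysis would add little: numbers are small, the authors themselves call the study underpowered, and the results are already printed. This stands as a limit on precision and as a reason for the post hoc label. It does not justify leaving a stated objective with no matching analysis.

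Stronger readings are tempting, but the documents do not support them.
- *An arm-by-site interaction was required and is missing.* No objective asks whether the oxygen effect differs by site.
- *Volume by site is an untested objective.* Volume is tied to position in the objectives, and site is tied to neurological outcome and intensive care stay.
- *The opposite signs in Table 4 show an effect that reverses by site.* The posterior row has 9 against 9 patients and a printed p of 0.7943, and no test compares the rows.
- *The authors misused the subgroup p values.* The Discussion makes no site-specific claim; its efficacy conclusion is the overall volume result.

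**Conclusion.** The point holds as a mismatch between objectives and analysis. On the between-group reading, neither secondary objective has a planned or reported test. On the within-group reading, neurological outcome is unsplit, one of three named groups is unreported, and two of five procedure categories are covered. The primary comparison is not affected.

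The repairable part is supratentorial against infratentorial (46 against 24) for SICU stay and deterioration. This assumes that the lesion categories in Table 1 are the nearest match to the objective's groups. They are not the same as the procedure categories: 46 supratentorial lesions against 39 conventional anterior procedures, and 24 infratentorial lesions against 26 conventional posterior procedures. Sitting against supine cannot be repaired with one sitting patient.

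Tables 3 and 4 say nothing either way about whether the oxygen effect differs by procedure.

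**What to change.** Add the following to the Sample Size and Statistical Analysis section, labelled post hoc because the results have been seen.

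- **SICU stay:** compare supratentorial with infratentorial patients, adjusted for arm, by a rank-based method or on the log scale, with a 95% CI. State that the analysis is restricted to patients admitted to the SICU and that 8 of 26 conventional posterior fossa patients are absent from Table 4.
- **Neurological deterioration:** make the same comparison by an arm-stratified exact method or a simple arm-adjusted estimate, with a 95% CI. Sixteen events do not support a model with more terms.
- **Sitting against supine:** declare it not estimable (1 against 38) and describe the single sitting patient's data only.
- **Transsphenoidal/endoscopic:** state that no such group is reported.
- **Tables 3 and 4:** label them exploratory, and draw no conclusion from their separate p values about differing effects. If such a statement is wanted, report an arm-by-procedure interaction with its CI from patient-level data. If volume is modelled on the log scale, say how zero volumes are handled.

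The cost is a few lines of text and SAS code on data already collected. The downside is wide intervals and post hoc status. An interaction would be especially imprecise: for volume at the planning SD, its standard error is 40 × √(1/23 + 1/16 + 1/15 + 1/11) = 20.5 ml, giving about 13.5% power for a 17.4 ml difference in effects.
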